4.8.4. Vital Signs and Physical Examinations

Vital signs and physical examinations data will not be collected.

4.8.5. Concomitant Medications

Concomitant medications will be coded using the WHO Drug dictionary. Results will be tabulated by Anatomic Therapeutic Class (ATC) and preferred term.

Concomitant medications will be defined as those medications that were initiated after study drug administration or those that were ongoing at the time of study drug administration. If the start date or stop date of a medication is partially missing, the date will be compared as far as possible with the date of the start of administration of study drug. The medication will be assumed to be prior medication if it cannot be definitively shown that the medication did not start or continue during the treatment period.

Non-ocular prior and concomitant medications will be summarized by higher ATC level 3 (therapeutic subgroup) and preferred term by treatment group and overall in the SAF population. ATC Level 3 terms will be sorted alphabetically. Preferred terms will be sorted by descending frequency overall within ATC Level 3 term. Subjects receiving a particular medication or medication of ATC Level 3 will be counted once at the preferred term level and once at ATC Level 3.

Ocular prior and concomitant medications will be summarized at the eye level, separately for study and non-study eyes, and at the subject level by ATC Level 3 and preferred term by treatment group and overall in the SAF.

All concomitant medications information will be presented in the data listing.

Statistical Analysis Plan

Sponsor:	VivaVision Biotech, Inc.		
Protocol:	VVN001-CS-201		
Document Version No.:	V3.0	Document Date:	13-JAN-2022

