2.1. Synopsis of Study Design

This is a Phase 2a, multi-center, double-masked, randomized, vehicle-controlled, parallel-group study designed to evaluate the safety and tolerability and to explore the efficacy activity of VVN001 1% and 5% Ophthalmic solution versus vehicle in subjects with dry eye disease. Approximately 165 subjects who meet inclusion/exclusion criteria will be eligible for randomization in 1:1:1 ratio to one of the 3 treatment groups: VVN001 Ophthalmic solution 1%, 5% or vehicle.

The study will consist of two periods over 14-weeks total: screening/run-in period (Day -14 to Day -1), and treatment period (Day 1 to Day 84).

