2.1.3. Study Treatment

VVN001 Ophthalmic Solution 1%, 5% or Vehicle will be administered to the ocular surface twice daily as a single drop in each eye administered morning and evening. The first dose of Single-Masked Vehicle and the first dose of Double-Masked IP (VVN001 1%, 5% or Vehicle) will be self-administered in the morning dose for that day. Following Visit 1, the second dose of Single-Masked IP will be received in the evening for approximately 14 days. Following Visit 2, the subject will be instructed to self-administer the second dose of Double-Masked IP in the evening BID instilled into each eye bilaterally for approximately 84 days.

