4.2.8. Missing, Unused, and Spurious Data

Any missing, unused, or spurious data will be noted in the final clinical study report. Missing data will be handled as follows. Missing data for other data points not covered below will be left as missing.

Sponsor:	VivaVision Biotech, Inc.		
Protocol:	VVN001-CS-201		
Document Version No.:	V3.0	Document Date:	13-JAN-2022

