4.2.8.2. Missing Dates

If the start date/time of an AE is partially or completely missing, the date/time will be compared as far as possible with the date/time of the start of administration of study drug. The AE will be assumed to be treatment-emergent if it cannot be definitively shown that the AE did not occur or worsen during the treatment-emergent period (worst case approach). Listings will display the available date data.

The following general rules will be used:

- If the start time of an AE is missing but the start date is complete, an AE will only be excluded as being treatment-emergent if the start date is before the date of study drug administration or if the stop date/time is before study drug administration.
- If the start time and day are missing but the start month and year are complete, an AE will only be excluded as being treatment-emergent if the start month/year is before the month/year of study drug administration or if the stop date/time is before study drug administration.
- If the start day and month are missing but the start year is complete, an AE will only be excluded as being treatment-emergent if start year is before the year of study drug administration or if the stop date/time is before study drug administration.
- If the start date is completely missing, an AE will be considered treatment-emergent unless the stop date/time is before study drug administration.

The above general rules are applicable to the partially or completely missing worsening date/time of AE as well.

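### SAP 4.8.5 classes a partly dated medication as prior when on-treatment use cannot be ruled out, the reverse of the SAP's own rule for adverse events

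*SAP*

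**What the plan says.** SAP 4.8.5 counts as concomitant any medication begun after study drug administration, together with "those that were ongoing at the time of study drug administration". It then deals with incomplete dates. The trigger is "If the start date or stop date of a medication is partially missing", and the first step is that "the date will be compared as far as possible with the date of the start of administration of study drug". The paragraph ends with the default: the medication is "assumed to be prior medication if it cannot be definitively shown that the medication did not start or continue during the treatment period".

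For adverse events, SAP 4.2.8.2 has the same two steps, a date comparison as far as possible and then a default. The default there is: "The AE will be assumed to be treatment-emergent if it cannot be definitively shown that the AE did not occur or worsen" in the treatment-emergent period. The SAP labels this a worst-case approach.

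Protocol 4.11 requires start and stop dates for each medication but gives no rule for incomplete ones. SAP section 5 declares no departures from the protocol's analyses. Neither document gives a reason for treating medications and adverse events in opposite ways.

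**The concern.** The condition contains a double negative. If it cannot be shown that a drug was *not* used on treatment, on-treatment use remains possible. One expects a cautious rule to count such a drug as concomitant, and the adverse event rule does the equivalent. The medication rule does the opposite.

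Protocol 3.1 bars other topical eyedrops during the study, and the concomitant medication tables are where a reader of the study report would first look for other treatment taken alongside study drug. A rule that moves uncertain records out of those tables errs towards under-reporting. A programmer also faces two instructions in one paragraph, the definition and the default, that cannot both be followed for every record if the default is taken literally.

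**Working it through.** There is no stated figure to reproduce. The check is to apply both rules to the same partly dated records.

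**Definitions.** Let F be the date of first dose.

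- On-treatment use is *ruled out* if the latest possible stop date is before F.
- It is *proven* if the earliest possible start is after F, or the earliest possible stop is on or after F (a stop on the day of first dose is counted as ongoing).
- Otherwise the record is *unresolved*.

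The 4.8.5 sentence can be read in two ways. *Literal*: the default applies to every partly dated record that meets its condition, that is, every record not ruled out. *Sequential*: the date comparison settles what it can, and the default applies only to the remainder.

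**Illustration.** F is assumed to be 15 March 2021. The records are invented to show the logic and are not frequencies.

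| Start | Stop | On-treatment use | 4.8.5, literal | 4.8.5, sequential | Default as in 4.2.8.2 |
|---|---|---|---|---|---|
| 2020 | 2020 | ruled out | prior | prior | prior |
| Feb 2021 | Feb 2021 | ruled out | prior | prior | prior |
| Feb 2021 | Mar 2021 | unresolved | prior | prior | concomitant |
| Mar 2021 | Mar 2021 | unresolved | prior | prior | concomitant |
| 2021 | 2021 | unresolved | prior | prior | concomitant |
| Feb 2021 | blank, not marked ongoing | unresolved | prior | prior | concomitant |
| Apr 2021 | Apr 2021 | proven | prior | concomitant | concomitant |
| 2021 | 20 Apr 2021 | proven | prior | concomitant | concomitant |

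**Results.**

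1. Ruled-out records (2 of 8) are prior under every reading. For these, 4.8.5 and 4.2.8.2 do not conflict.
2. Unresolved records (4 of 8) are prior under both readings of 4.8.5 and concomitant under the adverse event construction. The reversal therefore does not depend on how the sentence is read.
3. Proven records (2 of 8) separate the readings. A drug started and stopped in April was begun after first dose, so it is concomitant by definition. It still cannot be shown *not* to have been used on treatment, so the literal sentence calls it prior. This is the internal contradiction.
4. Records classed differently from the 4.2.8.2 construction: 4 under the sequential reading, and 4 + 2 = 6 under the literal reading.

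**Which real records are exposed.** On the sequential reading there are two kinds. The first has a stop date known only to the month or year of first dose and a start not shown to be after first dose. The second has a partial start date not shown to be after first dose, a blank stop date and no ongoing mark. It triggers the rule through its start date. A partial start on a drug recorded as ongoing is concomitant on any possible date and is not at risk.

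**Which outputs change.** SAP 7.1 lists Tables 14.1.7.5 to 14.1.7.8 for concomitant medications, and unresolved records would be absent from these. Tables 14.1.7.1 to 14.1.7.4 carry the words *Prior* and *Concomitant* together in their titles. If these mean prior only, they gain the records. If they mean prior and concomitant together, they do not change.

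**The case against.** The strongest reply is that this is a drafting slip with almost no consequence. Much of that stands. Start and stop dates are collected (Protocol 4.11) and omissions are queried (Protocol 10.6.1), so few or no records may be left unresolved. Listing 16.2.9.7 covers both prior and concomitant medications.

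A second reply is that the worst-case label is given only to adverse events, so the SAP never commits medications to it. That is also right. The documents show a sentence at odds with its own paragraph and opposite to its counterpart. They do not show that concomitant is the only admissible default. Deleting *not* would also make the sentence coherent and would keep prior as the default.

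A third is that on the sequential reading proven on-treatment records stay concomitant, so the clash with the definition largely disappears. This is correct for the contradiction, but not for the reversal, which holds on either reading.

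Several stronger inferences are tempting, and the documents do not support them:

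- *That per-protocol membership or efficacy results are affected.* SAP 3.2 bases exclusion from the PPS on a separate deviation review before unmasking, and no efficacy model in SAP 4.7 uses the classification.
- *That all eight medication tables change.* This depends on the ambiguous titles of the first four.
- *That the section has no usable reference point, because SAP 2.1.3 refers to the run-in vehicle as Single-Masked IP.* The disputed sentence refers to the treatment period, which SAP 2.1 sets as Day 1 to Day 84, apart from the run-in. A tighter definition of *prior* and of the reference dose would be welcome detail, but its absence is not an error here.
- *That drugs with both dates wholly missing are misclassified.* The trigger covers partially missing dates only, and SAP 4.2.8 says: "Missing data for other data points not covered below will be left as missing".

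**Conclusion.** The point holds. As written, the default in SAP 4.8.5 classes as prior a partly dated medication whose on-treatment use cannot be excluded. That is the reverse of SAP 4.2.8.2 under the same condition. Read literally, it also contradicts the definition of concomitant medication in the same paragraph. Nothing else in the protocol or SAP repairs or explains this.

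The size is minor. The direction is towards understating possible on-treatment medication use in descriptive Safety Set tables. No hypothesis test, estimate or analysis population is shown to change, and the number of affected records cannot be derived from the documents. The conclusion that Tables 14.1.7.5 to 14.1.7.8 lose records assumes only that the sentence is programmed as it stands and that at least one unresolved record exists.

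**What to change.** In the last sentence of the missing-date rule in SAP 4.8.5, replace *prior medication* with *concomitant* and leave the rest unchanged. The default then matches SAP 4.2.8.2 and agrees with the definition above it. If the sponsor does intend prior as the default, the sentence should be reworded so that it no longer captures drugs proven to be on treatment, and the SAP should justify the difference from the adverse event rule.

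The cost is one wording change and one derivation flag, with no new data. The downside is that some drugs actually stopped before first dose, but with dates too incomplete to show it, will be counted as concomitant. That is the conservative direction the SAP already accepts for adverse events.

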5. CHANGES TO PLANNED ANALYSES

As of this date, there have been no changes between the protocol-defined statistical analyses and those presented in this statistical plan.

Statistical Analysis Plan

Sponsor:	VivaVision Biotech, Inc.		
Protocol:	VVN001-CS-201		
Document Version No.:	V3.0	Document Date:	13-JAN-2022

7. CLINICAL STUDY REPORT APPENDICES

7.1. Statistical Tables to be Generated

Tables

Number	Title
Table 14.1.1	Overall Disposition and Subject Accountability – All Subjects Screened
Table 14.1.2	Overview of Analysis Sets – All Subjects Randomized
Table 14.1.3	Major Protocol Deviations – FAS
Table 14.1.4	Demographic and Baseline Characteristics - FAS
Table 14.1.5	Ocular Characteristics at Screening - FAS
Table 14.1.6.1	Study Eye Ocular Medical History - FAS
Table 14.1.6.2	Non-Study Eye Ocular Medical History – FAS
Table 14.1.6.3	Subject Level (Both Eyes) Ocular Medical History - FAS
Table 14.1.6.4	Non-ocular Medical History – FAS
Table 14.1.7.1	Study Eye Ocular Prior Concomitant Medications - SAF
Table 14.1.7.2	Non-Study Eye Ocular Prior Concomitant Medications – SAF
Table 14.1.7.3	Subject Level (Both Eyes) Prior Ocular Concomitant Medications – SAF
Table 14.1.7.4	Non-ocular Prior Concomitant Medications – SAF
Table 14.1.7.5	Study Eye Ocular Concomitant Medications – SAF
Table 14.1.7.6	Non-Study Eye Ocular Concomitant Medications – SAF
Table 14.1.7.7	Subject Level (Both Eyes) Ocular Concomitant Medications - SAF
Table 14.1.7.8	Non-ocular Concomitant Medications – SAF
Table 14.1.8	Study Medication Exposure - SAF
Table 14.2.1.1	Summary of Individual Subregion of CFS and Change from Baseline on Study Eye by Visit – FAS
Table 14.2.1.2	Summary of Individual Subregion of CFS and Change from Baseline on Study Eye by Visit - PPS
Table 14.2.1.3	Summary of Individual Subregion of CFS and Change from Baseline on Non-Study Eye by Visit - FAS
Table 14.2.1.4	Summary of Individual Subregion of CFS and Change from Baseline on Non-Study Eye by Visit - PPS
Table 14.2.2.1	Repeated Measures Mixed Model for Change from Baseline (CFB) in Inferior Region of CFS (iCFS) on Study Eye on Day 84 – FAS
Table 14.2.2.2	Repeated Measures Mixed Model for Change from Baseline (CFB) in Inferior Region of CFS (iCFS) on Study Eye on Day 84 – PPS

Sponsor:	VivaVision Biotech, Inc.		
Protocol:	VVN001-CS-201		
Document Version No.:	V3.0	Document Date:	13-JAN-2022

Table 14.2.2.3	Repeated Measures Mixed Model for Change from Baseline (CFB) in Inferior Region of CFS (iCFS) on Non-Study Eye on Day 84 – FAS
Table 14.2.2.4	Repeated Measures Mixed Model for Change from Baseline (CFB) in Inferior Region of CFS (iCFS) on Non-Study Eye on Day 84 – PPS
Table 14.2.2.5	Sensitivity Analysis: ANCOVA with LOCF Imputation for Change from Baseline (CFB) in Inferior Region of CFS (iCFS) on Day 84 – FAS
Table 14.2.3.1	Summary of Eye Dryness VAS and Change from Baseline by Visit – FAS
Table 14.2.3.2	Summary of Eye Dryness VAS and Change from Baseline by Visit – PPS
Table 14.2.4.1	Summary of Total CFS (tCFS) Score and Change from Baseline on Study Eye by Visit – FAS
Table 14.2.4.2	Summary of Total CFS (tCFS) Score and Change from Baseline on Study Eye by Visit – PPS
Table 14.2.4.3	Summary of Total CFS (tCFS) Score and Change from Baseline on Non-Study Eye by Visit – FAS
Table 14.2.4.4	Summary of Total CFS (tCFS) Score and Change from Baseline on Non-Study Eye by Visit – PPS
Table 14.2.5.1	Summary of Eye Discomfort VAS and Change from Baseline by Visit – FAS
Table 14.2.5.2	Summary of Eye Discomfort VAS and Change from Baseline by Visit – PPS
Table 14.2.6.1	Summary of SANDE Global Score and Change from Baseline by Visit – FAS
Table 14.2.6.2	Summary of SANDE Global Score and Change from Baseline by Visit – PPS
Table 14.2.7.1	Summary of Schirmer Score (without Anesthesia) and Change from Baseline on Study Eye by Visit – FAS
Table 14.2.7.2	Summary of Schirmer Score (without Anesthesia) and Change from Baseline on Study Eye by Visit – PPS
Table 14.2.7.3	Summary of Schirmer Score (without Anesthesia) and Change from Baseline on Non-Study Eye by Visit – FAS
Table 14.2.7.4	Summary of Schirmer Score (without Anesthesia) and Change from Baseline on Non-Study Eye by Visit – PPS
Table 14.2.7.5	Achieving More than 10 mm Increase in Schirmer Score (without Anesthesia) from Baseline on Study Eye by Visit – FAS
Table 14.2.7.6	Achieving More than 10 mm Increase in Schirmer Score (without Anesthesia) from Baseline on Study Eye by Visit – PPS

Sponsor:	VivaVision Biotech, Inc.		
Protocol:	VVN001-CS-201		
Document Version No.:	V3.0	Document Date:	13-JAN-2022

Table 14.2.7.7	Achieving More than 10 mm Increase in Schirmer Score (without Anesthesia) from Baseline on Non-Study Eye by Visit – FAS
Table 14.2.7.8	Achieving More than 10 mm Increase in Schirmer Score (without Anesthesia) from Baseline on Non-Study Eye by Visit – PPS
Table 14.2.8.1	Repeated Measures Mixed Model for Change from Baseline (CFB) in Eye Dryness VAS by Visit – FAS
Table 14.2.8.2	Repeated Measures Mixed Model for Change from Baseline (CFB) in Eye Dryness VAS by Visit – PPS
Table 14.2.9.1	Repeated Measures Mixed Model for Change from Baseline (CFB) in Total CFS (tCFS) on Study Eye by Visit – FAS
Table 14.2.9.2	Repeated Measures Mixed Model for Change from Baseline (CFB) in Total CFS (tCFS) on Study Eye by Visit – PPS
Table 14.2.9.3	Repeated Measures Mixed Model for Change from Baseline (CFB) in Total CFS (tCFS) on Non-Study Eye by Visit – FAS
Table 14.2.9.4	Repeated Measures Mixed Model for Change from Baseline (CFB) in Total CFS (tCFS) on Non-Study Eye by Visit – PPS
Table 14.2.10.1	Repeated Measures Mixed Model for Change from Baseline (CFB) in Individual Subregion of CFS on Study Eye by Visit – FAS
Table 14.2.10.2	Repeated Measures Mixed Model for Change from Baseline (CFB) in Individual Subregion of CFS on Study Eye by Visit – PPS
Table 14.2.10.3	Repeated Measures Mixed Model for Change from Baseline (CFB) in Individual Subregion of CFS on Non-Study Eye by Visit – FAS
Table 14.2.10.4	Repeated Measures Mixed Model for Change from Baseline (CFB) in Individual Subregion of CFS on Non-Study Eye by Visit – PPS
Table 14.2.11.1	Repeated Measures Mixed Model for Change from Baseline (CFB) in Eye Discomfort VAS by Visit – FAS
Table 14.2.11.2	Repeated Measures Mixed Model for Change from Baseline (CFB) in Eye Discomfort VAS by Visit – PPS
Table 14.2.12.1	Repeated Measures Mixed Model for Change from Baseline (CFB) in SANDE Global Score by Visit – FAS
Table 14.2.12.2	Repeated Measures Mixed Model for Change from Baseline (CFB) in SANDE Global Score by Visit – PPS
Table 14.2.13.1	Repeated Measures Mixed Model for Change from Baseline (CFB) in Schirmer Score (without Anesthesia) on Study Eye by Visit – FAS
Table 14.2.13.2	Repeated Measures Mixed Model for Change from Baseline (CFB) in Schirmer Score (without Anesthesia) on Study Eye by Visit – PPS

Sponsor:	VivaVision Biotech, Inc.		
Protocol:	VVN001-CS-201		
Document Version No.:	V3.0	Document Date:	13-JAN-2022

Table 14.2.13.3	Repeated Measures Mixed Model for Change from Baseline (CFB) in Schirmer Score (without Anesthesia) on Non-Study Eye by Visit – FAS
Table 14.2.13.4	Repeated Measures Mixed Model for Change from Baseline (CFB) in Schirmer Score (without Anesthesia) on Non-Study Eye by Visit – PPS
Table 14.3.1.1	Overview of Ocular Treatment-Emergent Adverse Events (TEAEs) - SAF
Table 14.3.1.2	Overview of Non-Ocular Treatment-Emergent Adverse Events (TEAEs) – SAF
Table 14.3.2.1	Ocular Treatment-Emergent Adverse Events (TEAEs) by System Organ Class and Preferred Term - SAF
Table 14.3.2.2	Non-Ocular Treatment-Emergent Adverse Events (TEAEs) by System Organ Class and Preferred Term – SAF
Table 14.3.2.3	Ocular Serious Treatment-Emergent Adverse Events (TEAEs) by System Organ Class and Preferred Term – SAF
Table 14.3.2.4	Non-Ocular Serious Treatment-Emergent Adverse Events (TEAEs) by System Organ Class and Preferred Term – SAF
Table 14.3.3.1	The Most Severity of Ocular Treatment-Emergent Adverse Events (TEAEs) by System Organ Class and Preferred Term – SAF
Table 14.3.3.2	The Most Severity of Non-Ocular Treatment-Emergent Adverse Events (TEAEs) by System Organ Class and Preferred Term – SAF
Table 14.3.4.1	The Strongest Relationship of Ocular Treatment-Emergent Adverse Events (TEAEs) to Study Drug by System Organ Class and Preferred Term – SAF
Table 14.3.4.2	The Strongest Relationship of Non-Ocular Treatment-Emergent Adverse Events (TEAEs) to Study Drug by System Organ Class and Preferred Term – SAF
Table 14.3.5.1	Summary of Slit-Lamp Biomicroscopy Results on Study Eye by Location and Visit – SAF
Table 14.3.5.2	Summary of Slit-Lamp Biomicroscopy Results on Non-Study Eye by Location and Visit – SAF
Table 14.3.6.1	Summary of Dilated Ophthalmoscopy Results on Study Eye by Visit – SAF
Table 14.3.6.2	Summary of Dilated Ophthalmoscopy Results on Non-Study Eye by Visit – SAF
Table 14.3.7.1	Summary of Intraocular Pressure (mmHg) Results and Change from Baseline on Study Eye by Visit – SAF
Table 14.3.7.2	Summary of Intraocular Pressure (mmHg) Results and Change from Baseline on Non-Study Eye by Visit – SAF
Table 14.3.8.1	Summary of Best Corrected Visual Acuity (BCVA) LogMAR Score and Change from Baseline on Study Eye by Visit – SAF

Statistical Analysis Plan

Sponsor:	VivaVision Biotech, Inc.		
Protocol:	VVN001-CS-201		
Document Version No.:	V3.0	Document Date:	13-JAN-2022

Table 14.3.8.2	Summary of Best Corrected Visual Acuity (BCVA) LogMAR Score and Change from Baseline on Non-Study Eye by Visit – SAF
Table 14.3.9.1	Achieving More than 10 mmHg Increase in Intraocular Pressure (IOP) from Baseline on Study Eye by Visit – SAF
Table 14.3.9.2	Achieving More than 10 mmHg Increase in Intraocular Pressure (IOP) from Baseline on Non-Study Eye by Visit – SAF
Table 14.3.10.1	Loss of More than 3 Lines in Best Corrected Visual Acuity (BCVA) LogMAR Score from Baseline on Study Eye by Visit – SAF
Table 14.3.10.2	Loss of More than 3 Lines in Best Corrected Visual Acuity (BCVA) LogMAR Score from Baseline on Non-Study Eye by Visit – SAF
Table 14.3.11	Summary of Comfort/Tolerability VAS and Change from Baseline by Visit – SAF
Table 14.3.12.1	Summary of Conjunctival Hyperemia Grading Scale on Study Eye by Visit – SAF
Table 14.3.12.2	Summary of Conjunctival Hyperemia Grading Scale on Non-Study Eye by Visit – SAF
Table 14.3.13.1	Summary of Hematology Results and Change from Screening by Visit – SAF
Table 14.3.13.2	Summary of Chemistry Results and Change from Screening by Visit – SAF
Table 14.3.13.3	Summary of Urinalysis Results and Change from Screening by Visit – SAF

Statistical Analysis Plan

Sponsor:	VivaVision Biotech, Inc.		
Protocol:	VVN001-CS-201		
Document Version No.:	V3.0	Document Date:	13-JAN-2022

